### **Study size**

Across the proposed databases, the source population for the study includes approximately 33.9 million subjects. All available data in each set will be used to identify vaccinated subjects. The size of the exposed population in this study will depend on the use of AZD1222, and the size of the comparator populations will depend on the pace of mass immunisation during the study period. The precision of risk estimates will depend on the background rate and the duration of vaccine-associated risk assumed for each AESI. For example, for Bell's palsy (background rate of 38 per 100,000 person-years and 42 days at risk per dose), with 1 million vaccinated subjects, we anticipate a 90% probability that the upper bound of the observed incidence rate ratio (IRR) would be below 2 assuming a 3-to-1 ratio between person-time for vaccinated subjects and concurrent unvaccinated comparators, respectively, and that the true IRR is 1.0 and a 100% probability that the upper bound of the observed IRR would be below 2, assuming a 1-to-1 ratio between person-time for vaccinated and active comparators or historical comparators, respectively, and that the true IRR is 1.0.

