ARS Toscana, Regional Health Agency of Tuscany; AZ, AstraZeneca; CIMS, COVID-19 vaccination Information and Monitoring System (Netherlands); COVID-19, coronavirus disease 2019; CPRD, Clinical Practice Research Datalink; ECDC, European Centre for Disease Prevention and Control; EU, European Union; FISABIO, Foundation for the Promotion of Health and Biomedical Research of Valencia Region; GP, general practitioner; PHARMO, PHARMO Database Network of the PHARMO Institute for Drug Outcomes Research; SIDIAP, Information System for Research in Primary Care; UK, United Kingdom; VID, Valencia Health System Integrated Database.

The precision of study results was estimated for each comparator cohort: concurrent unvaccinated, active comparators, and historical comparators. Additionally, a power estimation for the SCRI design analysis was performed. All calculations assumed that the true IRR between the AZD1222-vaccinated cohort and each comparator cohort was 1.0. All the

calculations estimated the probability that the upper bound of the 95% confidence interval (CI) around the observed IRR was below 1.5, 2.0, 2.5, and 3.0 for various study sizes and AESI rates. The ratio between AZD1222 and comparator person-time varied depending on the type of comparator.

First, the precision of the estimates for the comparison of **AZD1222-vaccinated subjects with concurrent unvaccinated subjects** was estimated assuming a 3:1 ratio for the person-time of AZD1222-vaccinated subjects to concurrent unvaccinated subjects. In Interim Report 1, the follow-up of subjects in the concurrent unvaccinated cohort was short, leading to a 2:1 ratio of person-time despite a 1:5 matching ratio. Results from Interim Report 2 included a longer follow-up and almost the same number of subjects vaccinated with AZD1222, since AZD1222 was no longer administered. The results suggested that the actual ratio of person-time is likely to be 3:1 in the final analysis, with some variations across data sources. The anticipated precision of the study was estimated for one of the least frequent AESIs, Guillain-Barré syndrome (GBS), assuming a background rate of 2 events per 100,000 person-years, 84 days at risk (42 days per dose). With a study size of 5 million vaccinated subjects, it was anticipated that there was a 75% probability that the upper bound of the 95% CI around the observed IRR would be below 3.0 ([Table 5](#)).

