### 9.7.7 Crude and Adjusted Measures of Association: Cohort Design

The analyses described below will address primary objective 4 and exploratory objectives 2.

- The analysis will compare subjects vaccinated with AZD1222 with the concurrent unvaccinated comparators and historical comparators to estimate the effect of receiving any dose (a first or a second), under the assumption that the effect of either dose is homogeneous. The effect of each individual dose on AESIs, will be estimated as prior vaccine exposure may “prime” the immune system.
- For outcomes that have **known risk windows**, we propose to estimate crude and adjusted IRRs and IR differences with 95% CIs using Poisson regression models. Specifically, the IRRs would be estimated using Poisson regression with robust estimation of the variance to account for individuals who may contribute person-time at different points to the exposed and unexposed cohorts (Zou 2004). For anaphylaxis and sudden death, crude and adjusted PPRs and PPDs with 95% CIs will be estimated using Poisson regression models with robust estimation of the variance to account for individuals who may contribute person-time to the exposed and unexposed cohorts at different timepoints.
- For outcomes **with unknown risk windows**, we propose estimating crude and adjusted relative risks and absolute risk differences. The relative risk (HRs) and 95% CI will be estimated using Cox regression models with robust estimation of the variance time-to-event analyses (Allison 2010). Using Cox regression models allows the flexibility to potentially adjust for time-dependant covariates, such as intercurrent COVID-19 infection.
- Adjustment for confounding will occur using PS, either through PS matching or by analytic methods involving stratification or weighting, which will be specified in the SAP. In the event that important covariates remain imbalanced after final selection of the cohorts for comparative analyses, additional approaches for confounding adjustment will be considered, including double-robust methods (ie, including the covariate in the outcome model as a separate term) or through analyses that restrict the population to subjects with more similar baseline characteristics (eg, subjects without substantial comorbidity).

The analysis described below will address exploratory objective 3

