**Multiple use of the same comparator:** In the PRAC assessment report for Interim Report 1 (Assessment Report for the Post-Authorisation Measure 007.6, 21 July 2022), the rapporteurs expressed concerns regarding the multiple use of the same concurrent unvaccinated subject based on the matching with replacement in a ratio of 1 AZD1222-vaccinated subject to 5 concurrent unvaccinated subjects. Based on the PRAC's suggestion, the matching ratio for AZD1222 to concurrent unvaccinated subjects was modified from 1:5 to 1:1. This measure reduced the number of times that a concurrent unvaccinated subject was matched. In the analysis for Interim Report 1, the percentage of comparators used only 1 time for matching ranged from 35% in CPRD to 60% in ARS Toscana, while in the analysis for Interim Report 2, it ranged from 65% in CPRD to 85% in ARS Toscana. Similarly, the percentage of comparators used 3 times or more ranged from 18% in ARS Toscana to 46% in CPRD in Interim Report 1, while in Interim Report 2, it ranged from 2% in ARS Toscana to 13% in CPRD (results for Interim Report 2 are preliminary). Robust estimation of the variance will be used to account for the remaining repeated matches to concurrent unvaccinated subjects, as well as to account for the repeated matches when using active comparators or historical comparators. PRAC Rapporteurs also expressed their concern about the use of general estimating equations (GEEs) taking into account only one of the sources of correlation to estimate the variance of the incidence rate ratio of AESIs and proposed the use of GEE methods with the combination of 3 covariance matrixes ([Austin and Cafri 2020](#), [Stuart 2010](#)). The 2 GEE methods together with bootstrapping will be evaluated for their use in the final study report. Bootstrapping may be considered if it is the only way to provide measures of uncertainty given the constraints of study size and issues with convergence.

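### Table 5 precision for the concurrent unvaccinated comparison treats comparators as independent although they are matched with replacement, so the stated 75% (GBS) and 90% (Bell's palsy) are too favourable by an amount the protocol does not let one fix

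*Protocol*

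**What the plan says.** Section 9.5 plans on precision rather than power. On the assumed effect it states: "All calculations assumed that the true IRR between the AZD1222-vaccinated cohort and each comparator cohort was 1.0". On the target quantity, which is tabulated over several study sizes and event rates, its wording is: "calculations estimated the probability that the upper bound of the 95% confidence interval (CI) around the observed IRR was below 1.5, 2.0, 2.5, and 3.0". Precision against the concurrent unvaccinated cohort "was estimated assuming a 3:1 ratio for the person-time of AZD1222-vaccinated subjects to concurrent unvaccinated subjects". For GBS (2 per 100,000 person-years, 84 days at risk, 5 million vaccinated) "it was anticipated that there was a 75% probability that the upper bound of the 95% CI around the observed IRR would be below 3.0". The abstract repeats the approach for Bell's palsy with 1 million vaccinated: "we anticipate a 90% probability that the upper bound of the observed incidence rate ratio (IRR) would be below 2".

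Section 9.2.1.1.3 fixes 1:1 matching with replacement. Section 9.9.1, under multiple use of the same comparator, gives the reuse. On the share of comparators used only once: "while in the analysis for Interim Report 2, it ranged from 65% in CPRD to 85% in ARS Toscana". On the share used three times or more: "in Interim Report 2, it ranged from 2% in ARS Toscana to 13% in CPRD". Both are labelled preliminary. The same section plans robust variance for the repeated matches and will evaluate two GEE methods and bootstrapping. Section 9.7.7 specifies "Poisson regression with robust estimation of the variance to account for individuals who may contribute person-time at different points" in the exposed and unexposed cohorts.

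**The concern.** The planned analysis allows for reuse of comparators, but the planned precision does not. If one unvaccinated person is matched to two or three vaccinees and has an event while those risk windows overlap, that single event enters the comparator count two or three times. The count then varies more than a Poisson count with the same mean. The robust interval will reflect this; the formula behind Table 5 does not. At 3:1 person-time the comparator arm contributes three quarters of the variance of the log IRR, so the inflation falls on the larger term.

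These are the headline precision figures for primary objective 4. A reader would use them to judge how far the study could rule out a given relative risk for a rare event, and would expect narrower intervals than the analysis will give.

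**Working it through.** **1. Reproduce the plan's figures.** Inputs from section 9.5, Table 5 and the abstract: true IRR 1, two-sided 95% interval, 84 days at risk, B = A/3. Rates per 100,000 person-years are 2 (GBS), 38 (Bell's palsy) and 100 (VTE).

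A = N × 84/365.25 × rate; SE = √(1/A + 1/B); P = Φ(ln U / SE − 1.96).

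- GBS, 5 million, U = 3.0: A = 23.0, B = 7.67, SE = 0.417, P = Φ(1.0986/0.417 − 1.96) = 0.750 (stated 0.75).
- Bell's palsy, 1 million, U = 2.0: A = 87.4, B = 29.1, SE = 0.214, P = 0.900 (stated 0.90).
- VTE, 1 million, U = 1.5: A = 230.0, B = 76.7, SE = 0.132, P = 0.867 (stated 0.87).

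All 48 cells of Table 5 reproduce within 0.005, so no design effect is in them. (The table's footnote gives a 1-to-4 ratio. That would put the GBS cell at 0.997; the printed values follow the 3:1 of the title.)

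**2. Design effect from the reported reuse.** Replace 1/B by D/B. Two assumptions are needed: comparators not in either reported group were used twice, and three or more means exactly three (which understates reuse). Let k be the number of uses.

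- CPRD (65/22/13%): mean k = 0.65 + 0.44 + 0.39 = 1.48; mean k² = 0.65 + 0.88 + 1.17 = 2.70.
- ARS Toscana (85/13/2%): mean k = 0.85 + 0.26 + 0.06 = 1.17; mean k² = 0.85 + 0.52 + 0.18 = 1.55.

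If the 3:1 ratio counts every matched copy and windows overlap fully, D = mean k² / mean k: 2.70/1.48 = 1.824 (CPRD) and 1.55/1.17 = 1.325 (ARS Toscana). CPRD supplies 3,938,490 of the 5,557,094 matched vaccinees in Table 4 (70.9%). Giving every other source the ARS Toscana pattern, D = 0.709 × 1.824 + 0.291 × 1.325 = 1.68.

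If the 3:1 ratio counts distinct person-time, only unequal use matters, and at full overlap D = mean k² / (mean k)²: 2.70/1.48² = 1.23 (CPRD) and 1.55/1.17² = 1.13 (ARS Toscana).

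If windows never overlap, D = 1. For partial overlap on the first reading, take D = 1 + f × 0.68, where f is the mean overlap. No value of f is given in the protocol.

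**3. Recompute.** Example, GBS at D = 1.68: SE = √(1/23.0 + 1.68/7.67) = 0.512; P = Φ(1.0986/0.512 − 1.96) = 0.57.

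| D | Assumption | GBS, 5 million, <3.0 | Bell's palsy, 1 million, <2.0 | VTE, 1 million, <1.5 | GBS, 5,557,094, <3.0 |
|---|---|---|---|---|---|
| 1.00 | none, as in Table 5 | 0.75 | 0.90 | 0.87 | 0.79 |
| 1.13 | distinct person-time, ARS Toscana pattern | 0.71 | 0.87 | 0.84 | 0.76 |
| 1.17 | every copy counted, f = 0.25 | 0.70 | 0.86 | 0.83 | 0.74 |
| 1.34 | every copy counted, f = 0.5 | 0.65 | 0.82 | 0.78 | 0.70 |
| 1.68 | every copy counted, f = 1 | 0.57 | 0.75 | 0.71 | 0.62 |

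At 5,557,094 vaccinees and D = 1.68, Bell's palsy still has probability 1.00 for <2.0 and 0.95 for <1.5, and VTE 1.00 for <1.5.

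**The case against.** Table 5 contains no arithmetic slip: each cell follows from the stated inputs and the cited method. What is missing is a design effect in a planning approximation. Reuse is disclosed, the matching ratio was cut from 1:5 to 1:1 because of it, and robust variance is planned. A reader might infer that the final intervals will be invalid; the protocol does not support that, since the defect lies in the forecast and not in the planned inference.

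The size is also open. The protocol does not say whether 3:1 counts repeated person-time, gives only two points of the reuse distribution, and gives nothing on window overlap. The short comparator follow-up (median under 2 months, section 9.1.1) does not settle the overlap, and neither does the mirrored second window in section 9.2.3.1. A reader might infer that a shortfall of five points or more is the expected case for GBS. That needs an assumed spread of index dates, and at 5,557,094 matched vaccinees an overlap of 0.25 gives 0.74, one point below the stated 0.75.

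A reader might also infer that more data sources are needed. Sections 9.5 and 9.7 do not support this: the study size is judged acceptable on the number of vaccinees and on reading estimates as continuous measures of varying precision. No probability threshold is set, and the same table accepts 0.38 for GBS below 2.0.

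These points limit the size and the consequence. They leave standing that the printed probabilities assume an independence which the design and section 9.9.1 rule out.

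**Conclusion.** The concern holds in direction. Table 5, the 75% GBS sentence and the 90% Bell's palsy sentence describe a comparison with independent comparators, and the planned comparison is not one. The probabilities are too high unless a reused comparator's risk windows never overlap.

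The size is a range, not a corrected value. It rests on assumed design effects of 1.13 to 1.68, built from preliminary reuse shares. These are not bounds: little overlap would bring D closer to 1, and heavier reuse than three times would raise it. Across that range, the stated-size figures lose about 4 to 18 points for GBS, 3 to 15 for Bell's palsy and 3 to 16 for VTE. The larger matched population recovers part of the GBS loss, and Bell's palsy and VTE remain precise at that size. The matter is worth correcting because the figures are headline statements for a primary objective, but it does not threaten the study's validity or the choice of data sources.

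**What to change.** Recompute Table 5, the GBS sentence in section 9.5 and the Bell's palsy sentence in the abstract with Var(log IRR) = 1/A + VIF/B. Take VIF in each data source from the Interim Report 2 reuse counts, counting repeated use only where a comparator's risk windows overlap. Alternatively, use the ratio of robust to model-based variance observed in Interim Report 2. State whether the 3:1 person-time ratio counts repeated person-time, and show a range of VIF rather than one value.

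The cost is a recalculation from data already held and text changes in section 9.5 and the abstract. The stated precision becomes somewhat less favourable. No new data are required.

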### **Data analysis**

Baseline characteristics of the subjects who received AZD1222 will be described overall and in sequential periods over time. Patterns of use of a second COVID-19 vaccine dose (AZD1222 and others) will be described.

For the cohort study, exposure propensity scores (PS) will be used to refine the balance between study cohorts, which will be matched initially on index date, age, sex, region, prior diagnosis of COVID-19, and status according to each of the 5 special populations, as applicable for each comparator. Propensity scores will be used to control for confounding either by analytic methods involving stratification or weighting. For AESIs with known risk windows, ie, for which the risk interval is characterised, crude IRs and 95% confidence intervals (CIs) for the vaccinated population and for the comparator cohorts will be estimated. Poisson regression models are proposed to estimate crude and adjusted IRRs and IR differences with 95% CIs comparing vaccinated and comparator cohorts. These analyses will combine all person-time at risk after dose 1 and dose 2 (if it was received). Exploratory analyses will report the IRs by specific dose. Comparative analysis between AZD1222 and active comparators will be limited to those with 2 doses of AZD1222 or an mRNA COVID-19 vaccine, and to the risk window after dose 2. For AESIs with unknown risk windows, cumulative incidence will be estimated using Kaplan-Meier methods starting after dose 1. Cox regression models are proposed to estimate crude and adjusted hazard ratios and 95% CIs.

For comparative analysis using the SCRI approach, conditional Poisson regression will be used to estimate IRRs and 95% CIs of specific AESIs with known risk windows, where appropriate.

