### Inclusion Criteria

#### AZD1222 Matched Cohort

Subjects in the **AZD1222 matched cohort** will include those subjects in the *all vaccinated first dose population* (ie, received at least 1 dose of AZD1222 within the study period, and this was their first COVID-19 vaccine dose) that fulfil *all* the following inclusion criteria:

- Have at least 12 months of data available before the index date
- Have no record of vaccination with any other COVID-19 vaccine on or before the index date

The **index date** will be the date when a subject receives the first AZD1222 dose within the study period.

For the comparison with the active comparator cohort, only AZD1222 vaccinees with a first and second dose of AZD1222 will be selected. The **index date** for this comparison will be the date of the second dose.

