The PRAC AR for Interim Report 1 (7 July 2022) requested that the MAH discuss the need for additional data sources. As per results from this Interim Report 1, 5.8 million subjects included in the study have received at least one dose of AZD1222. The number of AZD1222 vaccinees and data sources included in the current study at this time is considered acceptable for the purpose of interpreting findings as continuous measures that are estimated with varying degrees of precision ([Rothman and Greenland 2018](#)). Therefore, no additional data sources are considered necessary.

**Table 5 Probability That the Upper 95% Confidence Limit of the Observed IRR Will Be Below 1.5, 2, 2.5, and 3 for Various Study Sizes of Vaccinated Subjects, Assuming That the True RR is 1 and the Ratio of Vaccinated-to-Concurrent Unvaccinated Person-time is 3 to 1**

Adverse event (duration of risk interval after each dose)	Estimated background rate per 100,000 PY	People vaccinated	Upper confidence limit of IRR			
			1.5	2.0	2.5	3.0
Anaphylaxis (VAC4EU 2021, Willame et al 2021)	6	1,000,000	0.04	0.05	0.07	0.08
(3 days)	6	2,000,000	0.05	0.07	0.09	0.12
	6	3,000,000	0.05	0.09	0.12	0.16
	6	4,000,000	0.06	0.10	0.15	0.19
	6	5,000,000	0.07	0.12	0.17	0.23
GBS (VAC4EU 2021, Willame et al 2021)	2	1,000,000	0.06	0.11	0.16	0.22
(42 days)	2	2,000,000	0.09	0.18	0.28	0.38
	2	3,000,000	0.11	0.25	0.40	0.53
	2	4,000,000	0.14	0.32	0.50	0.65
	2	5,000,000	0.16	0.38	0.59	0.75
Bell's palsy (Morales et al 2013) (42 days)	38	1,000,000	0.47	0.90	0.99	1.00
VTE a (Heit 2015) (42 days)	100	1,000,000	0.87	1.00	1.00	1.00

a This adverse event is a constituent of the composite AESI “thrombosis.”

Note: Calculations assume a true IRR of 1.0 and a ratio of 1-to-4 exposed to unexposed person-years. Calculations also assume that each person contributes 6 days of follow-up for anaphylaxis (3-day risk interval x 2 doses), 56 days for stroke (28-day risk interval x 2 doses), and 84 days (42-day risk interval x 2 doses) for all other adverse events (Rothman and Greenland 2018). Calculations follow the method of Rothman and Greenland (2018).

AESI, adverse event of special interest; GBS, Guillain-Barré syndrome; IRR, incidence rate ratio; PY, person-years; RR, risk ratio; VAC4EU, Vaccine monitoring Collaboration for Europe; VTE, venous thromboembolism.

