Second, the precision for the results comparing **AZD1222-vaccinated subjects with active comparators and historical comparators** was estimated. The estimation of the precision of the results assumed a 1:1 ratio for the person-time of AZD1222-vaccinated subjects to active comparators and to historical controls (Kaura et al 2022). For one of the rarest anticipated events, GBS, assuming a background rate of 2 events per 100,000 person-years, 84 days at risk (42 days per dose), and a study size of 5 million vaccinated subjects, it was anticipated that there was a 96% probability that the upper bound of the 95% CI around the observed IRR would be below 3.0 (Table 6).

The number of AZD1222 vaccinees and data sources for the comparison of AZD1222 vaccinees with active and historical comparators is considered acceptable for the purpose of

interpreting findings as continuous measures that are estimated with varying degrees of precision. Assuming 1:1 ratio of matching will be achieved with the 5.8 million AZD1222 vaccinated subjects, no additional data sources are considered necessary.

**Table 6 Probability That the Upper 95% Confidence Limit of the Observed IRR Will Be Below 1.5, 2, 2.5, and 3 for Various Study Sizes of Vaccinated Subjects, Assuming That the True RR is 1 and the Ratio of Vaccinated Subjects to Active Comparators Person-time and to Historical Comparators Person-time is 1 to 1**

Adverse event (duration of risk interval after each dose)	Estimated background rate per 100,000 PY	People vaccinated	Upper confidence limit of IRR			
			1.5	2.0	2.5	3.0
Anaphylaxis (VAC4EU 2021, Willame et al 2021)	6	1,000,000	0.05	0.07	0.09	0.12
(3 days)	6	2,000,000	0.06	0.10	0.15	0.19
	6	3,000,000	0.07	0.13	0.20	0.27
	6	4,000,000	0.08	0.16	0.25	0.34
	6	5,000,000	0.09	0.19	0.30	0.41
GBS (VAC4EU 2021, Willame et al 2021)	2	1,000,000	0.09	0.18	0.28	0.38
(42 days)	2	2,000,000	0.14	0.32	0.50	0.65
	2	3,000,000	0.19	0.44	0.67	0.82
	2	4,000,000	0.23	0.56	0.79	0.92
	2	5,000,000	0.28	0.65	0.87	0.96
Bell's palsy (Morales et al 2013) (42 days)	38	1,000,000	0.76	1.00	1.00	1.00
VTE a (Heit 2015) (42 days)	100	1,000,000	0.99	1.00	1.00	1.00

a This adverse event is a constituent of the composite AESI “thrombosis.”

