Note: Calculations assume a true IRR of 1.0 and a ratio of 1-to-1 exposed to unexposed PY. Calculations also assume that each person contributes 6 days of follow-up for anaphylaxis (3-day risk interval x 2 doses), 56 days for stroke (28-day risk interval x 2 doses), and 84 days (42-day risk interval x 2 doses) for all other adverse events. Calculations follow the method of Rothman and Greenland (2018).

AESI, adverse event of special interest; GBS, Guillain-Barré syndrome; IRR, incidence rate ratio; PY, person-years; RR, risk ratio; VAC4EU, Vaccine monitoring Collaboration for Europe; VTE, venous thromboembolism.

Third, for the outcome of TTS, study size implications were evaluated in terms of precision of the absolute risk difference, rather than IRR, because the background risk for this newly described syndrome is unknown and conceivably could be zero (Table 7). Relative risks cannot be quantified when the risk in the reference group is zero. Moreover, effect measures in terms of absolute risk are preferred to relative risk to assess the public health impact of a safety concern and how it may factor into benefit-risk balance. Among vaccinated individuals,

the risk has been estimated from reporting rates, which have ranged between 1 per 100,000 and 1 per 250,000 per vaccinee (WHO 2021). The duration of the risk period for TTS is not known, but for this exercise, it has been assumed to be 4 weeks; based on case reports published by 11 May 2021, the onset of this outcome appears to occur within 4 weeks of vaccination (Greinacher et al 2021, Scully et al 2021). Table 7 shows the probability that the upper 95% confidence limit of the absolute risk difference for TTS will fall below various thresholds, across a range of different study sizes, assuming a 1-to-1 ratio of vaccinated to unvaccinated subjects. For example, assuming that the true 4-week risk of TTS is 1 per 100,000 vaccinees and that the background risk is zero, with 1,000,000 people vaccinated there is a 99% probability that the upper confidence limit of the absolute risk difference will fall below 3.0 per 100,000.

**Table 7 Probability That the Upper 95% Confidence Limit of the Observed 4-Week Absolute Risk Difference for TTS Will Be Below Various Thresholds for Different Study Sizes, Assuming that a True 4-Week Risk Among Vaccinees is 1 per 100,000 or 1 per 250,000**

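### Table 6 credits the active-comparator analysis with two risk windows per person, but that analysis counts only the window after dose 2, so its stated precision is too favourable

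*Protocol*

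**What the plan says.** Section 9.5 (Study Size) works out precision for the active and historical comparators in a single calculation, reported in Table 6. The Table 6 note reads "Calculations assume a true IRR of 1.0 and a ratio of 1-to-1 exposed to unexposed PY" and gives each person "84 days (42-day risk interval x 2 doses) for all other adverse events"; anaphylaxis gets 6 days (3 days x 2 doses). For GBS at 5 million the text concludes that "there was a 96% probability that the upper bound of the 95% CI around the observed IRR would be below 3.0". It then states that, if 1:1 matching is achieved for the 5.8 million AZD1222 vaccinees, no further data sources are needed for these two comparisons.

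The abstract (Study size) carries the same calculation forward for Bell's palsy at 1 million: "a 100% probability that the upper bound of the observed IRR would be below 2, assuming a 1-to-1 ratio between person-time for vaccinated" and active or historical comparators.

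The design of the active comparison is stated elsewhere. The abstract (Data analysis) says it is "limited to those with 2 doses of AZD1222 or an mRNA COVID-19 vaccine, and to the risk window after dose 2". Section 9.2.1.1.3 (AZD1222 Matched Cohort) says "For the comparison with the active comparator cohort, only AZD1222 vaccinees with a first and second dose of AZD1222 will be selected" and places the index date for this comparison at the second dose. The Active Comparators Cohort text in the same section does the same for mRNA recipients.

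**The concern.** Section 9.2.3.1 starts follow-up at the index date. When the index date is the second dose, the window after dose 1 lies before follow-up and cannot contribute person-time. Table 6 nevertheless counts it. Expected events in both cohorts are therefore twice what the active comparison can supply, and its probabilities of a bounded upper confidence limit are too high.

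At stake is the accuracy of a precision statement made to regulators. Section 9.5 records that PRAC asked whether additional data sources were needed, and the answer for the active comparison follows directly on the Table 6 figures.

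**Working it through.** **Inputs**
- True IRR 1.0 and 1:1 person-time: Table 6 note.
- Background rates per 100,000 person-years: GBS 2, Bell's palsy 38, anaphylaxis 6, VTE 100 (Table 6).
- Days per person as tabulated: 84, or 6 for anaphylaxis (Table 6 note).
- Days per person in the active comparison: 42, or 3 for anaphylaxis (one window after dose 2; abstract, Data analysis, and Section 9.2.1.1.3).
- 95% confidence limits, z = 1.96.

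**Formula**
- Expected events in the vaccinated cohort: e = N x (days / 365.25) x rate.
- Expected events in the comparator cohort: u = e divided by the person-time ratio.
- SE(log IRR) = sqrt(1/e + 1/u).
- P(upper limit < U) = Phi( ln U / SE - 1.96 ).

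**Step 1: reproduce the plan's figures (84 days, 1:1)**
- GBS, 5 million, U = 3: e = u = 5,000,000 x 84/365.25 x 2/100,000 = 23.0. SE = sqrt(2/23.0) = 0.295. P = Phi(1.0986/0.295 - 1.96) = 0.961. Stated: 96%.
- Bell's palsy, 1 million, U = 2: e = u = 87.4. SE = 0.151. P = 0.996. Stated: 100%.
- All 48 cells of Table 6 reproduce in this way, so the method is not in doubt.

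**Step 2: change only the days at risk**
- GBS, 5 million, U = 3: e = u = 11.5. SE = sqrt(2/11.5) = 0.417. P = Phi(1.0986/0.417 - 1.96) = 0.750.
- Bell's palsy, 1 million, U = 2: e = u = 43.7. SE = 0.214. P = 0.900.

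| Event, N, threshold | Table 6 (two windows) | One window after dose 2 |
|---|---|---|
| GBS, 5 million, < 3 | 0.96 | 0.75 |
| GBS, 5 million, < 2 | 0.65 | 0.38 |
| Bell's palsy, 1 million, < 2 | 1.00 | 0.90 |
| Bell's palsy, 1 million, < 1.5 | 0.76 | 0.47 |
| Anaphylaxis, 5 million, < 3 | 0.41 | 0.23 |
| VTE, 1 million, < 1.5 | 0.99 | 0.87 |

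**Step 3: relation to Table 5**

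Halving both cohorts at 1:1 gives variance 2/(e/2) = 4/e. Table 5, with 84 days at 3:1, has 1/e + 3/e = 4/e. The one-window values therefore equal those of Table 5. At the same N, the active comparison has no precision advantage over the concurrent unvaccinated one.

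**Step 4: dependence on the number matched**

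The 5.8 million in Section 9.5 are people with at least one dose. The protocol gives no number with two AZD1222 doses and an mRNA match, so the following N are assumptions. GBS, 42 days, U = 3:
- 5.8 million: 0.81
- 5 million: 0.75
- 4 million: 0.65
- 3 million: 0.53
- 2 million: 0.38
- 1 million: 0.22

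**Step 5: the Table 5 note**

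The note says "Calculations assume a true IRR of 1.0 and a ratio of 1-to-4 exposed to unexposed person-years", whereas the table title and the text of Section 9.5 say 3:1 vaccinated to unvaccinated. For GBS at 5 million and U = 3, 3:1 gives 0.750, as printed; 1-to-4 would give SE = sqrt(1.25/23.0) = 0.233 and P = 0.997. The note is the slip and the cells are right.

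**The case against.** The case for leaving this alone has several parts.

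- **Two windows are defined for mRNA recipients.** Section 9.2.3.1 gives two-dose recipients of AZD1222 or an mRNA vaccine a second risk window after the second dose. That text serves the analyses that start at dose 1. It does not rescue Table 6 for a comparison whose index date is dose 2.
- **The figures remain right for historical comparators.** This stands. That comparison combines the windows after both doses, so 96% and 100% hold there. A reader might infer that the two statements are simply wrong; they are wrong only for the active-comparator half of what they cover.
- **The protocol already accepts 75%.** This also stands. Section 9.5 reports 75% for GBS in the concurrent unvaccinated comparison, which serves primary objective 4, and considers the study size acceptable there. No target probability is set anywhere. A reader might infer that the data-source conclusion falls; the protocol does not support that if about 5 million two-dose recipients can be matched. With fewer, the precision is below the level it has accepted.
- **The analysis is exploratory and may not be run.** True. It is exploratory objective 3, no hypothesis is tested, all available data are used, and the observed intervals will carry the interpretation.
- **Limited overlap is disclosed.** Section 9.5 makes its conclusion conditional on 1:1 matching, Sections 9.1.1 and 9.9.1 discuss the poor age overlap, and Table 6 covers 1 to 5 million. That limits the complaint about N but does not touch the doubled days at risk.

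A reader might also infer that the feasibility decision would be taken against the inflated figures. Section 9.7.3.4 does not support this: it relies on covariate distributions, standardised differences, age-by-calendar-time overlap, the AUC and effective sample size, and does not refer to Table 6.

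**Conclusion.** The inconsistency is real. For the active comparison, Table 6 and the statements drawn from it count twice the person-time that the design allows. At unchanged N and 1:1 person-time, the GBS probability falls from 0.96 to 0.75 and the Bell's palsy probability from 1.00 to 0.90. The 0.75 itself assumes 5 million matched two-dose recipients, a number the protocol does not give. The approximation is the protocol's own and is rough for anaphylaxis, where one window at 5 million yields only about 2.5 expected events per cohort (5,000,000 x 3/365.25 x 6/100,000).

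This is a moderate error in planning figures for an exploratory analysis. The historical-comparator precision, the primary comparison and the analysis methods are unaffected.

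**What to change.** 1. Restrict Table 6, the 96% statement in Section 9.5 and the 100% statement in the abstract to historical comparators.
2. Add a separate active-comparator table with one window per person (42 days; 3 for anaphylaxis) over a range of matched two-dose recipients, for example 1 to 5.8 million.
3. Restate the sentence on additional data sources for the active comparison against that table. It can say that the precision equals what Section 9.5 already accepts for the concurrent unvaccinated comparison if about 5 million two-dose recipients can be matched, and is lower otherwise.
4. In the same edit, change the person-time ratio in the Table 5 note to 3:1 vaccinated to unvaccinated. This is a separate slip and alters no cell.

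The cost is a short recalculation and text edits. The stated precision for the active comparison becomes less favourable; nothing in the design or analysis has to change.
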